2.8.2 Laboratory data

Descriptive statistics will be generated for all clinical laboratory tests performed (actual values and changes from baseline) for three groups of laboratory tests (hematology, clinical chemistry and urinalysis) by laboratory test and treatment group. Change from baseline will only be summarized for patients with both baseline and post baseline values and will be calculated as:

$$\text{change from baseline} = \text{post baseline value} - \text{baseline value}$$

The following laboratory parameters will be analyzed for hematology test group: hemoglobin, platelets, white blood cell count, Reticulocytes, Haptoglobin, hematocrit, red blood cell (RBC) count, lymphocytes, lymphocytes (%), monocytes, monocytes (%), eosinophils eosinophils (%), neutrophils, neutrophils(%), basophils, and basophils (%).

The following laboratory parameters will be analyzed for Biochemistry test group: creatinine, total bilirubin (TBL), direct bilirubin, alanine aminotransferase (ALT), aspartate aminotransferase (AST), alkaline phosphatase (ALP), glucose, blood urea nitrogen (BUN). Sodium, potassium, calcium, creatinine, uric acid, gamma glutamyltransferase (GGT), magnesium, phosphate, chloride, and total protein, albumin, INR, Thyroid Stimulating hormone (TSH), Thyroxine Free T4.

Box plot for direct platelet count normalized using ULN (upper limit of normal) will be provided by timepoint and treatment group. Similarly, box plot for biochemistry parameters will also be provided by timepoint and treatment group. These Box plots will be presented using normalized values based on ULN and LLN (lower limit of normal) for all parameters with the exception of GGT, ALT, ALP, AST, BUN, direct bilirubin, total bilirubin Creatinine, and Urate, which are normalized using ULN only.

For liver enzymes (ALT, AST, etc.), the shift table of CTCAE grades relative to baseline will be provided. Summary with frequency and percentage of patients with liver related events as defined in [Table 2-2](#) will be provided by treatment:

Table 2-2 Liver-related events

Parameter	Criterion
ALT	>3xULN; >5xULN; >8xULN;>10xULN; > 20XULN
AST	>3xULN; >5xULN; >8xULN >10xULN; >20XULN
ALT or AST	>3xULN; >5xULN; >8xULN >10xULN>20XULN
ALT or AST and TBL	ALT or AST > 3 × ULN and TBL > 2 x ULN ALT or AST > 5 × ULN and TBL > 2 x ULN ALT or AST > 10 × ULN and TBL > 2 x ULN
TBL	>1.5xULN, >2xULN, >3XULN
ALP	>2xULN, >3xULN
ALP & TBL	ALP >3xULN & TBL >2xULN
(ALT or AST) & TBL & ALP	ALT or AST >3xULN & TBL >2xULN & ALP <2xULN (Hy's Law)

Listing of patients with the following renal related laboratories will be provided:

- Serum creatinine increase 25 – 49% compared to baseline

- Serum creatinine increase $\geq 50\%$ compared to baseline
- New dipstick proteinuria $\geq 1+$
- New dipstick hematuria $\geq 1+$

For urinalysis, frequency tables will be presented. Number and percent of patients in each category will be presented for each visit.

Urine pregnancy data will be summarized by visit.

Laboratory measurements, which are recorded as below the assay detection limits, will be imputed as half of the detection limit; and that above the detection limit will be imputed as detection limit, for the summary statistics.

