### 2.1 Objectives and related endpoints

**Table 2-1 Objectives and related endpoints (PK Run-in Part, Part A and Part B)**

Objective(s)	Endpoint (s)
Primary Objective(s)	Endpoint(s) for primary objective(s)

 
To determine the effective doses of KAF156 combined with LUM-SDF given
 
	
 
PCR-corrected adequate clinical and parasitological response (ACPR) at Day
 

Objective(s)	Endpoint (s)
daily over 1, 2 or 3 days for treatment of uncomplicated malaria caused by P. falciparum .	29 (i.e., 28 days post-dose) in Parts A and B. 

Assessments of KAF156 exposure in the PK Run-in cohort to understand the impact of LUM-SDF on KAF156 exposure.

Secondary Objective(s)	Endpoint(s) for secondary objective(s)

To evaluate the safety and tolerability of KAF156/LUM-SDF.

To further assess the effect of treatment with KAF156/LUM-SDF by assessing uncorrected ACPR and corrected ACPR at additional time points, as well as fever- and parasite clearance times.

To assess the key PK parameters of KAF156 and lumefantrine.

	

Standard safety/tolerability assessments: AE incidence and severity, liver and kidney function tests and electrocardiogram (ECG) abnormalities.

PCR-Uncorrected ACPR at Days 15, 29 and 43 (i.e., 14, 28 and 42 days post-dose). PCR-corrected ACPR at Days 15 and 43 (i.e., 14 and 42 days post-dose). Incidence rate of recrudescence and reinfection at Days 15, 29 and 43. Parasite and Fever Clearance Times (PCT and FCT). Proportion of patients with parasitaemia at 12, 24, and 48 hours after treatment.

PK assessments

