2.8.1.1 Adverse events of special interest / grouping of AEs

The adverse events of special interest are defined in the Case retrieval Sheet (CRS) which is updated for each MEDDRA dictionary. The CRS data are stored in RDCRS SAS dataset corresponding to a subset of eCRS SAS view for which the following filtering criteria are applied

-Drug code = KAF156

-the latest version of MedDRA at the time of final database lock.

-End date is null (this means this is the latest CRS version). Potential risks based on the current CRS are listed in [Table 2-1](#).

The number and percent of patients with these special AEs will be summarized. In addition, listings of related adverse events will be provided.

Newly occurring liver enzyme abnormalities and QTcF abnormalities will be summarized (see [Sections 2.8.2 and 2.8.3.1](#))

Table 2-1 List of safety topics of interest

Safety Topic Of Interest	SOC	Search Criteria Details	MedDRA Code	MedDRA Term	MedDRA Level	MedDRA Qualifier
Gastrointestinal tolerability	Gastrointestinal disorders		20000140	Gastrointestinal nonspecific symptoms and therapeutic procedures (SMQ)	MQ2	BROAD
Bradycardia	Cardiac disorders		90003924	Bradycardia [KAF156] (CMQ)	NMQ1	
Gastrointestinal bleeding and ulceration	Gastrointestinal disorders		90003929	Gastrointestinal bleeding and ulceration [KAF156] (CMQ)	NMQ1	
Renal tubular necrosis	Renal and urinary disorders		90003925	Renal tubular necrosis [KAF156] (CMQ)	NMQ1	
Thyroid hypertrophy and hyperplasia	Endocrine disorders		90003926	Thyroid hypertrophy and hyperplasia [KAF156] (CMQ)	NMQ1	
Hepatotoxicity (GenMed)	Hepatobiliary disorders	ALT/AST > 3 ULN; ALP > 2 ULN; TBL>1.5 ULN; ALP >3 ULN and TBL>2 ULN; ALT/ AST > 3 ULN and TBL>2 ULN; ALT/AST > 3 ULN and TBL >= 2 ULN and ALP <2 ULN'	20000006	Drug related hepatic disorders – comprehensive search (SMQ)	MQ2	BROAD
QTc prolongation	Cardiac disorders	Number of pts with notable QTcF, those with QTcF>500 msec, or increase by >=60 msec over baseline. Sustained ventricular tachycardia lasting 30 sec or more, or ventricular fibrillation	20000001	Torsade de pointes/QT prolongation (SMQ)	MQ1	BROAD

Hematological disorders	Blood and lymphatic system disorders		20000027	Haematopoietic cytopenias (SMQ)	MQ1	BROAD
Antimalarial drug resistance	Infections and infestations		90003928	Anti-malarial drug resistance [KAF156] (CMQ)	NMQ1	
Drug – Drug Interactions	General disorders and administration site conditions		90000024	Interactions (PSUR) [STANDARD] (NMQ)	NMQ1	

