2.8.3 Other safety data

2.8.3.1 ECG and cardiac imaging data

The following quantitative variables will be summarized for averaged triplicate ECG: heart rate, RR interval, PR interval, QRS interval, QT interval, QTcB (QT interval corrected for heart rate according to Bazett) and QTcF (QT interval corrected for heart rate according to Fredericia).

Descriptive summary statistics for the change from baseline for each post-baseline visit will be performed by ECG parameters and treatment group.

Patients with notably high QT, HR and fever ($\geq 37.5^\circ\text{C}$ for *axillary* or $\geq 38.3^\circ\text{C}$ for other routes) will be provided.

To assess the temporal correlations mean change of QTcF over time, mean change of ECG HR over time, mean change of temperature over time, and PK concentration of KAF156 and lumefantrine over time will be plotted with all panels aligned on the x-axis (Time after dosing).

QTc will be summarized categorically by computing the number and percentage of patients at each time point and at the maximum post baseline value with following:

- QT, QTcF, or QTcB
 - > 450 and ≤ 480 ms
 - > 480 and ≤ 500 ms
 - > 500 ms
 - Increase from Baseline of ≥ 30 ms to < 60 ms
 - Increase from Baseline of ≥ 60 ms
- HR for age ≥ 18 years
 - Increase from baseline $>25\%$ and to a value > 100 bpm
 - Decrease from baseline $>25\%$ and to a value < 50 bpm
- HR for age < 18 years
 - $>$ upper limit of normal (ULN) defined in Table 2-3
 - $<$ lower limit of normal (LLN) defined in Table 2-3
- PR

- Increase from baseline >25% and to a value > 200 ms
- New value of > 200 ms
- QRS
 - Increase from baseline >25% and to a value > 120 ms
 - > 120 ms

Table 2-3 Normal heart rates (resting) by age

Age (years)	Normal range bpm
1 - ≤ 3	70 - 110
3 - ≤ 6	65 -110
6 - ≤12	60 -95
>12	55 -85

Source: Nelson Textbook of Pediatrics, 18th Edition

A line plot by patient (Spaghetti plot) will be provided by visit and treatment group.

In addition, shift tables comparing baseline ECG results (normal, abnormal, not available, total) with the post-baseline results will be provided by visit and at the worst post-baseline result (normal, abnormal, not available, total).

A listing of all newly occurring or worsening abnormalities as compared with baseline will be provided, as well as a by-patient listing of all quantitative ECG parameters.

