2.8.3.2 Vital signs

The following quantitative variables will be summarized: Weight (kg), Temperature (°C), Pulse (beats/min), Supine systolic blood pressure (mmHg) and Supine diastolic blood pressure (mmHg).

Analysis in vital sign measurement using descriptive summary statistics for the change from baseline for each post-baseline visit will be performed by vital sign and treatment group. Change from baseline will only be summarized for patients with both baseline and post-baseline values and will be calculated as:

$$\text{Change from baseline} = \text{post-baseline value} - \text{baseline value}$$

As body temperature is being measured using different routes, in order to harmonize all temperature values, for summaries a correction will be made to methods other than axillary as follows.

$$\text{Body temperature (axillary equivalent)} = \text{value (oral/tympanic/rectal)} - 0.5 \text{ degrees } (^\circ\text{C}).$$

The number and percentage of patients with newly occurring notable vital signs will be presented. Criteria for notable vital sign abnormalities are provided in [Table 2-4](#) below.

Table 2-4 Criteria for notable vital sign abnormalities

Vital sign (unit)	Notable abnormalities
Systolic blood pressure (mmHg) for age ≥ 18 years	≥ 180 mmHg/ ≤ 90 mmHg with increase/decrease from baseline of ≥ 20 mmHg
Systolic blood pressure (mmHg) for age < 18 years	$>$ ULN or $<$ LLN defined in Table 2-5
Diastolic blood pressure (mmHg) for age ≥ 18 years	≥ 105 mmHg/ ≤ 50 mmHg with increase/decrease from baseline of ≥ 15 mmHg
Diastolic blood pressure (mmHg) for age < 18 years	$>$ ULN or $<$ LLN defined in Table 2-5
Pulse (beats/min) for age ≥ 18 years	≥ 120 bpm/ ≤ 50 bpm with increase/decrease from baseline of ≥ 15 bpm
Pulse (beats/min) for age < 18 years	$>$ ULN or $<$ LLN defined in Table 2-3
Temperature ($^{\circ}\text{C}$)	≥ 37.5 (axillary) or ≥ 38.0 (other routes)
Weight	decrease $> 7\%$ from Baseline increase $> 7\%$ from Baseline

A listing of all newly occurring or worsening abnormalities as compared with baseline will be provided, as well as a by-patient listing of all vital signs.

Table 2-5 Normal blood pressure by age

Age (years)	Normal range systolic (mmhg)	Normal range diastolic (mmhg)
1 - ≤ 3	90-105	55-70
3 - ≤ 6	95-110	60-75
6 - ≤ 12	100-120	60-75
> 12 - < 18	110-135	65-85

[figure not shown]
Source: Nelson Textbook of Pediatrics, 18th Edition

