2.15 Interim analysis

PK Run-in Part: For the patients in the PK Run-in KAF156 200 mg/LUM-SDF 960 mg cohort, PK analyses will be performed on the samples collected in the first 24 hours. AUC_{0-24} , for KAF156 and lumefantrine will be calculated and compared with the expected values when one drug was given alone. Dosing in Part A will subsequently proceed according to the algorithm specified in protocol, Table 3-1.

End of Part A: After the last patient has completed the last visit in Part A, the clinical database will be cleaned and locked.

An interim assessment will be performed to evaluate if any KAF156 and LUM-SDF combination is effective and safe and which KAF156 and LUM-SDF dose regimen(s) will be carried forward in Part B. Only the primary efficacy endpoint, selected secondary efficacy (uncorrected ACPR at Day 29, PCT, and FCT), PK, and safety endpoints (all adverse events, serious adverse events and laboratory results) will be analyzed by the study biostatistics team. Other efficacy and safety endpoints will be analyzed if deemed necessary.

The results will be communicated to relevant internal and external people who will contribute to the selection of effective and safe dose regimen.

DMC reports: At selected time points during the study, DMC reports will be provided by a CRO team not involved in the study conduct. The unblinded DMC reports will be reviewed by the DMC.

Additional ad-hoc safety review may be requested by DMC or Novartis if needed. Only the decision or information needed for planning/modifying the trial (such as continuation of study, dosing information for new patients, etc.) will be communicated to the blind clinical trial team involved in trial conduct. No further dissemination of DMC reports should occur.

Below is the outline of the data required for the DMC review.

Table 2-8 Specification of data outputs for DMC data review

Output	Analysis set	Periodic safety review	End of Part A interim analysis
Baseline			
Patient disposition	Randomized	Yes	Yes
Recruitment by country and center	Randomized	Yes	Yes
Demographic characteristics	Randomized	Yes	Yes
Background disease characteristics	Randomized	Yes	Yes
Safety			
Concomitant medications/significant non-drug therapies	Safety	Yes	Yes
All adverse events and Serious adverse events (including narratives)	Safety	Yes	Yes
General, liver, and renal specific safety laboratories (categorical analysis)	Safety	Yes	Yes
ECG (Categorical analysis)	Safety	Yes	Yes

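### SAP 2.8.2 reports its four renal laboratory criteria only as a patient listing; a by-arm count with proper denominators would be a cheap improvement

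*SAP*

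**What the plan says.** Protocol Table 2-1, repeated in SAP Table 1-1, includes "liver and kidney function tests and electrocardiogram (ECG) abnormalities" among the endpoints for the secondary safety objective.

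SAP 2.8.2 names the four renal criteria and gives them one output: "Listing of patients with the following renal related laboratories will be provided". Other threshold criteria in the SAP are counted:

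- Liver, in the same section: "Summary with frequency and percentage of patients with liver related events", by treatment.
- ECG, SAP 2.8.3.1: "QTc will be summarized categorically by computing the number and percentage of patients at each time point", and also at the maximum post-baseline value.
- Vital signs, SAP 2.8.3.2: "The number and percentage of patients with newly occurring notable vital signs will be presented".

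SAP Table 2-7 follows the same pattern. It has rows with a categorical summary for liver, ECG and vital-sign abnormalities, and no row for renal abnormalities. SAP Table 2-8 does list "General, liver, and renal specific safety laboratories (categorical analysis", but as an output for the data monitoring committee.

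**The concern.** A listing identifies patients but does not compare arms. Part A has six KAF156/LUM-SDF regimens and Coartem, and the purpose is to choose among doses. For renal laboratory findings the reader would have to count cases by hand. The reader would also have to find denominators that the listing does not contain: patients with both a baseline and a post-baseline value and, for the dipstick criteria, those negative at baseline.

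Adverse event tables cannot be relied on instead. Under protocol 7.1 an abnormal laboratory value becomes an adverse event only if it causes signs or symptoms, is judged clinically significant, or needs therapy. An asymptomatic creatinine rise or dipstick change can meet the SAP's criterion and never reach those tables.

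**Working it through.** The plan states no figure to reproduce. The check is whether another planned output already gives the any-time, by-arm incidence of the four criteria.

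**1. Change-from-baseline summaries and box plots (SAP 2.8.2).** These describe distributions and do not count patients over a threshold. The creatinine box plots are scaled to the upper limit of normal (ULN), not to the patient's own baseline. A rise by a factor f stays at or below ULN when baseline ≤ ULN/f:

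- 25% rise: 1/1.25 = 0.80 × ULN
- 50% rise: 1/1.50 = 0.67 × ULN

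A patient starting below these values can meet the criterion and still plot at or below 1.

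**2. Urinalysis frequency tables (SAP 2.8.2).** These give number and percent per category at each visit, which is prevalence and not new onset. Illustration with assumed counts: 50 patients, 5 positive for protein at baseline, 3 others newly positive at one visit, and r of the 5 resolved by then. The per-visit table changes by (3 − r)/50, that is +6, +4, +2 or 0 percentage points for r = 0, 1, 2, 3. The new-onset incidence is 3/45 = 6.7% (exact 95% CI 1.4% to 18.3%) in every case. Varying the assumed number positive at baseline:

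| Baseline positives of 50 | New onset | Exact 95% CI |
|---|---|---|
| 0 | 3/50 = 6.0% | 1.25% to 16.55% |
| 5 | 3/45 = 6.7% | 1.40% to 18.27% |
| 10 | 3/40 = 7.5% | 1.57% to 20.39% |

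**3. By-visit selection (SAP Table 5-7).** By-visit summaries use the value closest to the target day. Protocol Table 16-1 asks for repeat tests at 24-48 hours and follow-up at 2-5 days, so off-schedule values are expected and a peak can be left out.

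**4. Adverse events of special interest (SAP 2.8.1.1).** Renal tubular necrosis is a safety topic and its adverse events are counted, but by a term search. The sentence on laboratory and ECG abnormalities there reads "Newly occurring liver enzyme abnormalities and QTcF abnormalities will be summarized" and does not mention renal values.

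**5. Data monitoring committee tables (SAP Table 2-8).** A categorical renal laboratory analysis is planned for periodic review and for the end of Part A. Its criteria are not stated, and SAP 2.15 does not allow the committee's reports to circulate further.

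**6. CTCAE grading (SAP 5.5).** This may cover part of creatinine. It relies on an internal grading document that is not in the public files, so the extent cannot be judged.

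**Size of the hand count.** Part A: 4 criteria × 7 arms = 28 figures. Part B: up to 4 × 4 = 16. Pooled A+B: up to 4 × 4 = 16. PK run-in: 4 × 1 = 4. Total: up to 64.

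**Precision available.** With no events in n patients, the exact upper limit is 1 − 0.025^(1/n): 7.1% for n = 50 and 13.7% for n = 25.

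**The case against.** The SAP follows the protocol here. Protocol 9.5.2 asks for categorical summaries of liver enzymes, notable vital signs and ECG values, and for none of the renal criteria. Kidney function is already summarized by arm through descriptive statistics and change from baseline, and dipstick categories are counted per visit. The committee receives a categorical renal analysis at the end of Part A, and protocol Table 3-2 gives it and the sponsor the judgement of cohort safety. The remaining gap is therefore in the study report. All of this stands and limits the point to an improvement.

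The strongest objection concerns the fix. The SAP's four criteria are not the protocol's full event definitions. Protocol 7.4 wants the creatinine rise confirmed after at least 24 hours and during normal hydration. Table 16-1 asks for proteinuria to be confirmed at 24-48 hours and excludes hematuria due to trauma or menstruation. A raw any-time count would include cases that fail these conditions. That stands as well, and the fix must allow for it.

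Two stronger inferences are not supported:

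- A reader might infer that the protocol's low/normal/high laboratory shift tables (9.5.2.2) have been dropped, because SAP 2.8.2 does not restate them. However, the SAP's introduction says that it implements the protocol's analysis, SAP 2.1 refers to protocol section 9, and SAP section 4 declares no changes. Read together, these keep the tables planned.
- A reader might take the blank search-criteria cell for renal tubular necrosis in SAP Table 2-1 as a renal-specific omission. Eight of the ten topics there have a blank cell, including bradycardia, although low heart rate is counted elsewhere.

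**Conclusion.** The point holds as a minor improvement to reporting. None of the four renal criteria in SAP 2.8.2 has a stated by-arm count, and no other planned study-report output supplies the any-time incidence. The gap is clearest for creatinine; for protein and blood, per-visit dipstick counts give partial cover. It would be wrong to call this a departure from the protocol, or to say that the SAP has no categorical renal output at all, given the committee tables.

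No estimate or dose decision is shown to change. With arms of about 50 and 25 the intervals are wide, so the counts would be descriptive. The proteinuria example rests on assumed counts and only shows why per-visit prevalence and new onset differ. The conclusion also assumes that the unseen CTCAE grading document does not already lead to an equivalent table.

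**What to change.** In SAP 2.8.2, add one descriptive table per part, and for pooled Parts A and B, giving n (%) by treatment group for each of the four criteria:

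- Count a patient who meets the criterion at any post-baseline time, including unscheduled values.
- Use patients with a baseline and at least one post-baseline value as the denominator; for proteinuria and hematuria, restrict it to those negative at baseline.
- Label the rows as meeting the laboratory threshold, not as renal events.
- Show separately the creatinine rises of 25% or more confirmed after at least 24 hours (protocol 7.4) and the proteinuria confirmed on repeat (protocol Table 16-1).
- Keep the listing for case review of hydration status and of hematuria due to menstruation or trauma.

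The cost is a few extra tables on data already collected. A renal categorical output is already planned for the committee, and SAP Table 5-7 already has a most-extreme-value rule for notable laboratory abnormalities. The drawback is more tables with wide intervals, which should be presented without formal comparison.

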2.8.3 Other safety data

2.8.3.1 ECG and cardiac imaging data

The following quantitative variables will be summarized for averaged triplicate ECG: heart rate, RR interval, PR interval, QRS interval, QT interval, QTcB (QT interval corrected for heart rate according to Bazett) and QTcF (QT interval corrected for heart rate according to Fredericia).

Descriptive summary statistics for the change from baseline for each post-baseline visit will be performed by ECG parameters and treatment group.

Patients with notably high QT, HR and fever ($\geq 37.5^\circ\text{C}$ for *axillary* or $\geq 38.3^\circ\text{C}$ for other routes) will be provided.

To assess the temporal correlations mean change of QTcF over time, mean change of ECG HR over time, mean change of temperature over time, and PK concentration of KAF156 and lumefantrine over time will be plotted with all panels aligned on the x-axis (Time after dosing).

QTc will be summarized categorically by computing the number and percentage of patients at each time point and at the maximum post baseline value with following:

- QT, QTcF, or QTcB
 - > 450 and ≤ 480 ms
 - > 480 and ≤ 500 ms
 - > 500 ms
 - Increase from Baseline of ≥ 30 ms to < 60 ms
 - Increase from Baseline of ≥ 60 ms
- HR for age ≥ 18 years
 - Increase from baseline $>25\%$ and to a value > 100 bpm
 - Decrease from baseline $>25\%$ and to a value < 50 bpm
- HR for age < 18 years
 - $>$ upper limit of normal (ULN) defined in Table 2-3
 - $<$ lower limit of normal (LLN) defined in Table 2-3
- PR

- Increase from baseline >25% and to a value > 200 ms
- New value of > 200 ms
- QRS
 - Increase from baseline >25% and to a value > 120 ms
 - > 120 ms

Table 2-3 Normal heart rates (resting) by age

Age (years)	Normal range bpm
1 - ≤ 3	70 - 110
3 - ≤ 6	65 -110
6 - ≤12	60 -95
>12	55 -85

Source: Nelson Textbook of Pediatrics, 18th Edition

A line plot by patient (Spaghetti plot) will be provided by visit and treatment group.

In addition, shift tables comparing baseline ECG results (normal, abnormal, not available, total) with the post-baseline results will be provided by visit and at the worst post-baseline result (normal, abnormal, not available, total).

A listing of all newly occurring or worsening abnormalities as compared with baseline will be provided, as well as a by-patient listing of all quantitative ECG parameters.

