2.1.1.1 Definition of treatment failures

Early Treatment Failures (ETF)

Patient will be classified as ETF upon meeting any of the following criterion

- Development of danger signs or severe malaria on Day 2, Day 3, Day 4 in the presence of parasitemia.
- Parasitemia on Day 3 higher than Day 1 count irrespective of axillary temperature.
- Parasitemia on Day 4 with axillary temperature $\geq 37.5^{\circ}\text{C}$.
- Parasitemia on Day 4 equals to or more than 25% of count on Day 1.

Late Clinical Failure (LCF)

Patient will be classified as LCF upon meeting any of the following criterion

- Development of danger signs or severe malaria on any day from Day 5 to Day 43 in the presence of parasitemia without previously meeting any of the criteria of early treatment failure.
- Presence of parasitemia and axillary temperature $\geq 37.5^{\circ}\text{C}$ on any day from Day 5 to Day 43 without previously meeting any of the criteria of Early Treatment Failure.

Late Parasitological Failure (LPF)

- Presence of parasitemia on any day from Day 8 to Day 43 and axillary temperature $< 37.5^{\circ}\text{C}$ without previously meeting any of the criteria of Early Treatment Failure or Late Clinical Failure. Missing body temperature assessment in presence of parasitemia will be classified as LCF.

Note: If the temperature is measured using other routes, such as oral/tympanic/rectal, the corresponding threshold for fever is 38.0°C . Danger signs or severe malaria is recorded as adverse events. The adverse event start date of danger signs or severe malaria will be used in the determination of ETF and LCF. Only *P. Falciparum* asexual form is used for parasitemia/parasite in the assessments of treatment failure and ACPR in [Section 2.1.1.2](#) below. The body temperature assessment closest to the blood smear assessment date will be used.

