2.3.2 Patient demographics and other baseline characteristics

Demographic data and baseline disease characteristics will be descriptively presented and tabulated per treatment group, as well as overall, using randomized set and PPS. If many patients are excluded from randomized set, summary will also be provided for the FAS.

Following demographic variables will be summarized

- Age and age categories (for Part B: 2 to <6, 6 to <12 ; for PK run-in cohort and and Part A: <12, 12 to <18, 18 to <65, and ≥ 65 , <18 vs ≥ 18 yrs)
- Sex (male, female)
- Patient child bearing status (able to bear children, premenarche, post menopausal, sterile of child bearing age)
- Race (Caucasian, black, Asian, native american, pacific islander, unknown, other)
- Ethnicity
- Body weight and weight categories (<35, 35 to <75 and ≥ 75 kg for Part A and PK run-in cohort); (10 to <15, 15 to <25, 25 to <35 and ≥ 35 kg for Part B);(<15 , 15 to <25, 25 to <35, 35 to 75, >75 kg for Parts A+B)
- Body height (cm)
- BMI and BMI categories (<16, 16 to 25, >25) (Kg/m^2)

Following disease characteristics at baseline will be summarized

- Body temperature and categories (<37.5, 37.5 to <39, ≥ 39) ($^{\circ}\text{C}$) for (*axillary*) and <38.0 $^{\circ}\text{C}$, 38.0 to 39.5, ≥ 39.5 for other routes)

- Falciparum species: (P. Falciparum asexual forms, P. Falciparum gametocytes, P. Vivax, P. Ovale, P. malariae, P. Knowlesi, and Mixed-infection , n (%))
- P. falciparum density per micro ltr. and its categories (<1,000, 1,000 to <2,000, 2,000 to <5,000, 5,000 to <15,000, 15,000 to <50,000, 50,000 to <100,000, 100,000 to <150,000, >=150,000 parasites/ μ L; <100,000 / μ L, \geq 100,000 parasites / μ L)
- Gametocytes counts / μ L.

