2.7 Analysis of secondary efficacy objective(s)

2.7.1 Secondary endpoints

Secondary efficacy variables include:

1. PCR-corrected ACPR at Days 15 and 43;
2. Uncorrected ACPR at Days 15, 29, and 43;

3. Proportion of patients with parasitemia at 12, 24, and 48 hours after treatment;
4. Time to parasite clearance (PCT), defined as time from the first dose until the first total and continued disappearance of (*P. Falciparum*) asexual parasite forms which remained at least a further 48 hours;
5. Time to fever clearance (FCT), defined as time from the first dose until the first time the axillary body temperature decreased below and remained below 37.5°C axillary or 38.0°C oral/tympanic/rectal for at least a further 24 hours;
6. Proportion of patients with early treatment failure (ETF);
7. Proportion of patients with late clinical failure (LCF);
8. Proportion of patients with late parasitological failure (LPF);
9. Incidence rate of recrudescence and reinfection at Days 15, 29 and 43.

Analyses of ACPRs (PCR corrected or uncorrected) will be based on the FAS and PPS. Analyses of other secondary efficacy variables will be based on the FAS.

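### SAP 2.8.3.1 sets fever at 38.3 °C for non-axillary routes in the QT, heart-rate and fever output, against 38.0 °C everywhere else; a minor inconsistency to align

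*SAP*

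**What the plan says.** SAP Section 2.8.3.1 (ECG and cardiac imaging data) announces an output on "Patients with notably high QT, HR and fever". The fever limit is 37.5 °C for axillary readings "or $\geq 38.3^\circ\text{C}$ for other routes) will be provided".

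Elsewhere the SAP pairs 37.5 °C axillary with 38.0 °C for other routes:

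- Table 2-4 in Section 2.8.3.2 takes as notable a temperature "≥ 37.5 (axillary) or ≥ 38.0 (other routes").
- The note to the treatment-failure definitions in Section 2.1.1.1 says that for other routes, "such as oral/tympanic/rectal, the corresponding threshold for fever is" 38.0 °C.
- Fever clearance time in Section 2.7.1 uses "37.5°C axillary or 38.0°C oral/tympanic/rectal for at least a further 24 hours", and the fever clearance definition in Section 2.1.1.2 uses the same pair.
- The baseline categories in Section 2.3.2 split other-route readings below 38.0 °C, then "38.0 to 39.5, ≥ 39.5 for other routes".

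The protocol uses the same pair in inclusion criterion 4, in Section 6.5.3 and in Section 9.5.1.

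Section 2.8.3.2 also gives a conversion, stated for summaries: axillary equivalent equals the oral, tympanic or rectal reading minus 0.5 °C.

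**The concern.** The two limits in Section 2.8.3.1 do not describe the same degree of fever. Any rule covering several routes needs different numbers for each route, so a difference is expected in itself. The trouble is that this pair is 0.8 °C apart, while every other pair in the documents is 0.5 °C apart.

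Programmed as written, the rule makes inclusion in a safety output depend partly on where the thermometer was placed. QTc prolongation is a safety topic of interest in SAP Table 2-1, and Section 2.8.3.1 also plots QTcF, heart rate, temperature and drug concentration on a common time axis. Temperature is therefore part of how the SAP reads the ECG findings, and the fever limit used alongside them should match the one used in the rest of the analysis.

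**Working it through.** No sample-size, power or error-rate figure is involved. The check sets the cut-offs side by side and applies the SAP's conversion.

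**Cut-offs**

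| Place | Axillary | Other routes | Difference |
|---|---|---|---|
| SAP 2.8.3.1, QT/HR/fever output | 37.5 °C | 38.3 °C | 0.8 °C |
| SAP Table 2-4, notable vital signs | 37.5 °C | 38.0 °C | 0.5 °C |
| SAP 2.1.1.1, treatment-failure note | 37.5 °C | 38.0 °C | 0.5 °C |
| SAP 2.1.1.2 and 2.7.1, fever clearance | 37.5 °C | 38.0 °C | 0.5 °C |
| SAP 2.3.2, lower baseline boundary | 37.5 °C | 38.0 °C | 0.5 °C |
| SAP 2.3.2, upper baseline boundary | 39 °C | 39.5 °C | 0.5 °C |
| Protocol 4.1, 6.5.3 and 9.5.1 | 37.5 °C | 38.0 °C | 0.5 °C |

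**Expected other-route limit.** Axillary equivalent = other-route reading − 0.5 °C. Solving for the reading that matches the axillary limit gives 37.5 + 0.5 = 38.0 °C. The stated 38.3 °C is not reproduced.

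**What 38.3 °C means on the axillary scale.** 38.3 − 0.5 = 37.8 °C. The excess over the axillary limit is 37.8 − 37.5 = 0.3 °C.

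**Readings classified differently** (assuming temperatures are recorded to one decimal, which the documents do not state)

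| Other-route reading | Axillary equivalent | Fever elsewhere in the SAP | Fever in the 2.8.3.1 output |
|---|---|---|---|
| 38.0 °C | 37.5 °C | yes | no |
| 38.1 °C | 37.6 °C | yes | no |
| 38.2 °C | 37.7 °C | yes | no |
| 38.3 °C | 37.8 °C | yes | yes |

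Without the one-decimal assumption, the gap is every non-axillary reading from 38.0 °C up to but not including 38.3 °C.

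**Who is omitted.** All three conditions must hold: the patient meets the QT and heart-rate condition; the relevant temperatures were taken by a non-axillary route; and the highest of them lies in that gap. The documents give no figure for the share of non-axillary readings, so no count can be derived. SAP 2.8.3.2 does say that temperature is measured by different routes, so the situation can arise.

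**The case against.** The best case on the other side concerns consequence rather than text, and most of it stands.

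- A reader might infer that febrile patients at 38.0 to 38.2 °C drop out of the QTc safety analysis. The documents do not support that. The output names QT with heart rate and fever, on its natural reading all three together, so fever alone puts nobody in it. The categorical tables for QT, QTcF and QTcB in the same section carry no temperature condition.
- A reader might infer that safety information is lost. It is not. Section 2.8.3.1 also provides the aligned plots, a listing of new or worsening ECG abnormalities and a by-patient listing of all quantitative ECG parameters, and Section 2.8.3.2 adds a by-patient listing of all vital signs. Coinciding fever and ECG findings can be recovered from these at any cut-off.
- A reader might infer that this output will contradict the vital-signs table patient by patient because of the cut-off. The Table 2-4 summary counts newly occurring abnormalities and this output has no such restriction, so the two could differ even with identical limits.
- The SAP does not call the output a listing, does not state its purpose and does not say how temperature and ECG are matched in time. The 0.5 °C conversion is stated for summaries of vital signs, so using it here is an extension.

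The last point does not rescue 38.3 °C: the mismatch is visible from the cut-offs alone, without the conversion. A deliberately stricter definition of fever would be expected to raise the axillary limit too, and it stays at 37.5 °C. The change histories also suggest an oversight, since the SAP log and Protocol Amendment 2 both record work to harmonise temperature limits across routes; that is an inference about intent, not proof.

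**Conclusion.** The inconsistency is real. One operative definition in SAP 2.8.3.1 departs from all other non-axillary fever cut-offs in both documents, by 0.3 °C, without explanation. It is not an arithmetic error: no calculation in the SAP is wrong.

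Severity is minor. The effect is confined to one output and to the patients described above, in unknown and possibly zero number. This rests on reading the output as requiring QT, heart-rate and fever findings together. The primary endpoint and fever clearance time use the 38.0 °C limit and do not change.

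**What to change.** In SAP 2.8.3.1, replace 38.3 °C with 38.0 °C for other routes. Alternatively, convert all readings to axillary equivalents and apply the single 37.5 °C limit. If 38.3 °C was intended, say why and explain why the axillary limit was left at 37.5 °C. Since the whole point turns on one digit, confirm it in the signed SAP before editing.

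The cost is one number in the SAP and one program line. If the output has already been produced, rerun it. No data collection or clinical rule changes.
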